Appendix 4 Clinical Laboratory CTCAE Grading

Investigations				
Grade				
Laboratory Analyte	1	2	3	4
aPTT (activated partial thromboplastin time) prolonged	>ULN - 1.5 x ULN	>1.5 – 2.5 x ULN	>2.5 x ULN	-
Alanine aminotransferase increased	>ULN – 3.0 x ULN if baseline was normal; 1.5 - 3.0 x baseline if baseline was abnormal	>3.0 – 5.0 x ULN if baseline was normal; >3.0 - 5.0 x baseline if baseline was abnormal	>5.0 – 20.0 x ULN if baseline was normal; >5.0 - 20.0 x baseline if baseline was abnormal	>20.0 x ULN if baseline was normal; >20.0 x baseline if baseline was abnormal
Alkaline phosphatase increased	>ULN – 2.5 x ULN if baseline was normal; 2.0 - 2.5 x baseline if baseline was abnormal	>2.5 – 5.0 x ULN if baseline was normal; >2.5 - 5.0 x baseline if baseline was abnormal	>5.0 – 20.0 x ULN if baseline was normal; >5.0 - 20.0 x baseline if baseline was abnormal	>20.0 x ULN if baseline was normal; >20.0 x baseline if baseline was abnormal
Aspartate aminotransferase increased	>ULN – 3.0 x ULN if baseline was normal; 1.5 - 3.0 x baseline if baseline was abnormal	>3.0 – 5.0 x ULN if baseline was normal; >3.0 - 5.0 x baseline if baseline was abnormal	>5.0 – 20.0 x ULN if baseline was normal; >5.0 - 20.0 x baseline if baseline was abnormal	>20.0 x ULN if baseline was normal; >20.0 x baseline if baseline was abnormal
Blood bilirubin increased	>ULN – 1.5 x ULN if baseline was normal; > 1.0 - 1.5 x baseline if baseline was abnormal	>1.5 – 3.0 x ULN if baseline was normal; >1.5 - 3.0 x baseline if baseline was abnormal	>3.0 – 10.0 x ULN if baseline was normal; >3.0 - 10.0 x baseline if baseline was abnormal	>10.0 x ULN if baseline was normal; >10.0 x baseline if baseline was abnormal
Creatinine increased	>ULN -1.5 x ULN	>1.5 – 3.0 x baseline; >1.5 -3.0 x ULN	>3.0 baseline; >3.0 – 6.0 xULN	>6.0 x ULN
GGT (gamma-glutamyl transferase) increased	>ULN – 2.5 x ULN if baseline was normal; 2.0 - 2.5 x baseline if baseline was abnormal	>2.5 – 5.0 x ULN if baseline was normal; >2.5 - 5.0 x baseline if baseline was abnormal	>5.0 – 20.0 x ULN if baseline was normal; >5.0 - 20.0 x baseline if baseline was abnormal	>20.0 x ULN if baseline was normal; >20.0 x baseline if baseline was abnormal
Hemoglobin increased (a)	Increase in >0 – 2 gm/dL above ULN (a)	Increase in >2 – 4 gm/dL above ULN (a)	Increase in >4 gm/dL above ULN (a)	n/a

Investigations				
Laboratory Analyte	Grade			
	1	2	3	4
Anemia (hemoglobin decreased)	LLN- 10g/dL; <LLN – 6.2 mmol/L; <LLN – 100 g/L	<10.0 – 8.0 g/dL; <6.2 – 4.9 mmol/L; <100 – 80g/L	<8.0 g/dL; <4.9 mmol/L; <80 g/L; transfusion indicated	Life-threatening consequences; urgent intervention indicated
INR increased	>1.2 – 1.5; >1 -1.5 x baseline if on anticoagulation (use of anticoagulation identified using the B01A ATC code)	>1.5 – 2.5; >1.5 – 2.5 x baseline if on anticoagulation (use of anticoagulation identified using the B01A ATC code)	>2.5; >2.5 x baseline if on anticoagulation (use of anticoagulation identified using the B01A ATC code)	-
Neutrophil count decreased	<LLN - 1500/mm3; <LLN - 1.5 x 10e9 /L	<1500 - 1000/mm3; <1.5 - 1.0 x 10e9 /L	<1000 - 500/mm3; <1.0 - 0.5 x 10e9 /L	<500/mm3; <0.5 x 10e9 /L
Lymphocyte count decreased	<LLN - 800/mm3; <LLN - 0.8 x 10e9/L	<800 - 500/mm3; <0.8 - 0.5 x 10e9 /L	<500 - 200/mm3; <0.5 - 0.2 x 10e9 /L	<200/mm3; <0.2 x 10e9 /L
Lymphocyte count increased	-	>4000/mm3 - 20,000/mm3	>20,000/mm3	-
Platelet count decreased	<LLN - 75,000/mm3; <LLN - 75.0 x 10 ⁹ /L	<75,000 - 50,000/mm3; <75.0 - 50.0 x 10 ⁹ /L	<50,000 - 25,000/mm3; <50.0 - 25.0 x 10 ⁹ /L	<25,000/mm3; <25.0 x 10 ⁹ /L
White blood cell decreased	<LLN – 3000/mm ³ ; <LLN – 3.0 x 10 ⁹ /L	<3000 – 2000/mm ³ ; <3.0 – 2.0 x 10 ⁹ /L	<2000 – 1000/mm ³ ; <2.0 – 1.0 x 10 ⁹ /L	<1000/mm ³ ; <1.0 x 10 ⁹ /L
(a) Definition: A finding based on laboratory test results that indicate increased levels of hemoglobin above normal – i.e. above ULN.				

Metabolism and Nutrition Disorders				
Adverse Event	Grade			
	1	2	3	4
Hypercalcemia (Calcium Increased)	Corrected serum calcium of >ULN - 11.5 mg/dL; >ULN - 2.9 mmol/L; Ionized calcium >ULN - 1.5 mmol/L	Corrected serum calcium of >11.5 - 12.5 mg/dL; >2.9 - 3.1 mmol/L; Ionized calcium >1.5 - 1.6 mmol/L; symptomatic	Corrected serum calcium of >12.5 - 13.5 mg/dL; >3.1 - 3.4 mmol/L; Ionized calcium >1.6 - 1.8 mmol/L; hospitalization indicated	Corrected serum calcium of >13.5 mg/dL; >3.4 mmol/L; Ionized calcium >1.8 mmol/L; life-threatening consequences
Hyperkalemia (Potassium Increased)	>ULN - 5.5 mmol/L	>5.5 - 6.0 mmol/L; intervention initiated	>6.0 - 7.0 mmol/L; hospitalization indicated	>7.0 mmol/L; life-threatening consequences
Hypermagnesemia (Magnesium Increased)	>ULN - 3.0 mg/dL; >ULN - 1.23 mmol/L	n/a	>3.0 - 8.0 mg/dL; >1.23 - 3.30 mmol/L	>8.0 mg/dL; >3.30 mmol/L; life-threatening consequences
Hypernatremia (Sodium Increased)	>ULN - 150 mmol/L	>150 - 155 mmol/L; intervention initiated	>155 - 160 mmol/L; hospitalization indicated	>160 mmol/L; life-threatening consequences
Hypoalbuminemia (Albumin Decreased)	<LLN - 3 g/dL; <LLN - 30 g/L	<3 - 2 g/dL; <30 - 20 g/L	<2 g/dL; <20 g/L	Life-threatening consequences; urgent intervention indicated
Hypocalcemia (Calcium Decreased)	Corrected serum calcium of <LLN - 8.0 mg/dL; <LLN - 2.0 mmol/L; Ionized calcium <LLN - 1.0 mmol/L	Corrected serum calcium of <8.0 - 7.0 mg/dL; <2.0 - 1.75 mmol/L; Ionized calcium <1.0- 0.9 mmol/L; symptomatic	Corrected serum calcium of <7.0 - 6.0 mg/dL; <1.75 - 1.5 mmol/L; Ionized calcium <0.9- 0.8 mmol/L; hospitalization indicated	Corrected serum calcium of <6.0 mg/dL; <1.5 mmol/L; Ionized calcium <0.8 mmol/L; life-threatening consequences
Hypoglycemia (Glucose Decreased)	<LLN - 55 mg/dL; <LLN - 3.0 mmol/L	<55 - 40 mg/dL; <3.0 - 2.2 mmol/L	<40 - 30 mg/dL; <2.2 - 1.7 mmol/L	<30 mg/dL; <1.7 mmol/L; life-threatening consequences; seizures
Hypokalemia (Potassium Decreased)	<LLN - 3.0 mmol/L	Symptomatic with <LLN - 3.0 mmol/L; intervention indicated	<3.0 - 2.5 mmol/L; hospitalization indicated	<2.5 mmol/L; life-threatening consequences
Hypomagnesemia (Magnesium Decreased)	<LLN - 1.2 mg/dL; <LLN - 0.5 mmol/L	<1.2 - 0.9 mg/dL; <0.5 - 0.4 mmol/L	<0.9 - 0.7 mg/dL; <0.4 - 0.3 mmol/L	<0.7 mg/dL; <0.3 mmol/L; life-threatening consequences
Hyponatremia (Sodium Decreased)	<LLN - 130 mmol/L	125-129 mmol/L and asymptomatic	125-129 mmol/L symptomatic; 120-124 mmol/L regardless of symptoms	<120 mmol/L; life-threatening consequences

Renal and Urinary Disorders				
	Grade			
Adverse Event	1	2	3	4
Chronic kidney disease	eGFR (estimated Glomerular Filtration Rate) or CrCl (creatinine clearance) <LLN - 60 ml/min/1.73 m ² or proteinuria 2+ present; urine protein/creatinine >0.5	eGFR or CrCl 59 - 30 ml/min/1.73 m ²	eGFR or CrCl 29 - 15 ml/min/1.73 m ²	eGFR or CrCl <15 ml/min/1.73 m ² ; dialysis or renal transplant indicated

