- A male or female subject who is of reproductive potential agrees to remain truly abstinent or use (or have their partner use) acceptable methods of highly effective contraception starting from the time of consent through 3 months after the completion of study therapy. True abstinence is defined as abstinence that is in line with the preferred and usual lifestyle of the subject. Periodic abstinence (e.g., calendar, ovulation, symptothermal, post-ovulation methods), declaration of abstinence for the duration of the study, and withdrawal are not acceptable methods of contraception. Acceptable methods of highly effective birth control are combined or progesterone-only hormonal contraception that is associated with inhibition of ovulation, intrauterine device, and intrauterine hormone-releasing system.

9. Subjects receiving hydroxyurea must have received it continuously for at least 6 months prior to signing the ICF, and must have been on a stable dose for at least 3 months prior to signing the ICF, with no anticipated need for dose adjustments during the study including the screening period, in the opinion of the investigator.

10. **For NTDT subjects only:** Subjects must have Hb  $\leq 10.0$  g/dL at Screening; the screening Hb sample must be collected 7 to 28 days prior to randomization. Hb values within 21 days post-transfusion will be excluded.

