9.0 Study Endpoints, Variables and Covariates

Primary Endpoints	TDT	NTDT
IMR-687 safety and tolerability assessed using: 
• Incidence and severity of adverse events and serious adverse events• Incidence of subjects with a post-Baseline clinically significant worsening in the CTCAE laboratory grade for a lab parameter	X	X

 Incidence of subjects with a post-Baseline clinically significant change in a vital signs parameter Incidence of subjects meeting the clinically significant criteria for an electrocardiogram (ECG) parameter Changes from Baseline in 12-lead ECG clinical laboratory test (chemistry, hematology, coagulation, and urinalysis), and vital signs parameters (continuous parameters only) Changes in physical examination findings relative to the Baseline physical examination 		
Secondary Endpoints	TDT	NTDT
Proportion of subjects with a $\geq 20\%$ reduction in RBC transfusion burden with a reduction of at least 2 units of RBCs (hematological improvement) for Week 12 to Week 24 and Week 24 to Week 36, compared to the 12 weeks prior to Baseline (Day 1).	X	
Proportion of subjects with a $\geq 20\%$ reduction in RBC transfusion burden with a reduction of at least 2 units of RBCs (hematological improvement) for Week 12 to Week 36, compared to the 12 weeks prior to Baseline (Day 1).	X	
Proportion of subjects with a $\geq 20\%$ reduction in RBC transfusion burden with a reduction of at least 2 units of RBCs (hematological improvement) for any 12-week rolling time period – Day 2 to 85, Day 3 to 86, etc. through Day 170 to Day 253 (Week 36) – compared to the 12 weeks prior to Baseline (Day 1).	X	
Proportion of subjects with a $\geq 20\%$ reduction in RBC transfusion burden with a reduction of at least 2 units of RBCs (hematological improvement) for any 14-week rolling time period – Day 2 to 99, Day 3 to 100, etc. through Day 156 to Day 253 (Week 36) – compared to the 12 weeks prior to Baseline (Day 1).	X	
Proportion of subjects with a $\geq 33\%$ reduction in RBC transfusion burden with a reduction of at least 2 units of RBCs (hematological improvement) for Week 12 to Week 24 and Week 24 to Week 36, compared to the 12 weeks prior to Baseline (Day 1).	X	
Proportion of subjects with a $\geq 33\%$ reduction in RBC transfusion burden with a reduction of at least 2 units of RBCs (hematological improvement) for Week 12 to Week 36, compared to the 12 weeks prior to Baseline (Day 1).	X	

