Urinalysis assessments include: appearance, color, pH, specific gravity, ketones, protein, glucose, bilirubin, and urobilinogen, including occult blood and microscopic examination of sediment (only if occult blood is detected).

Shift tables will be used to summarize the shift from Baseline grade to maximum CTCAE grade (Grade 1 to 4 and Missing) for selected hematology and chemistry parameters listed in Appendix 4, by treatment arm and the combined IMR-687 treatment arms and presented separately for each population. Any subject with a post-Baseline result meeting the criteria, including those collected at unscheduled visits, will be included in the tabulation.

Potentially clinically significant (PCS) Criteria for hepatic function and renal function are shown in Table 5 below. The number and percentage of subjects meeting these PCS criteria will be summarized for hepatic function parameters (ALT, AST, ALP, and total bilirubin), the renal function parameter (serum creatinine), and platelet count separately. Any subject with any post-baseline result (including "unscheduled" visits) meeting the criteria will be included in the tabulation.

Table 5 PCS Criteria for Hepatic Function, Renal Function, and Platelet Count

Hepatic Function	Renal Function	Platelet Count

 ○ Post-baseline Alanine Aminotransferase (ALT) $\geq 3 \times$ upper limit of normal (ULN) ○ Post-baseline Aspartate Aminotransferase (AST) $\geq 3 \times$ ULN ○ Post-baseline Direct Bilirubin (BILDIR) $\geq 2 \times$ ULN ○ Post-baseline ALT/AST and BILDIR (ALT $\geq 3 \times$ ULN or AST $\geq 3 \times$ ULN) and BILDIR $\geq 2 \times$ ULN (Hy's Law) 	
 ○ Post-baseline Creatinine Clearance (CREATCLR) $< 0.5 \times$ baseline ○ Post-baseline Serum Creatinine (CREAT) $> 2 \times$ baseline 	
 ○ Post-baseline Platelet Count $> 1000 \times 10^9/L$

The following figures will be provided for the following hematology, chemistry, and coagulation results: MCV, platelets, neutrophils, reticulocyte (absolute and percent), GGT, LDH, creatinine, AST, ALT, indirect bilirubin, ACR.

- Shift plot from baseline to post-baseline maximum value for each parameter by treatment arm and for the combined IMR-687 treatment arms;
- Box and whisker plot for each lab parameter by visit for each treatment arm and the combined IMR-687 treatment arms.

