The number and percentage of subjects meeting the following selected change in Hb categories will be tabulated by treatment arm:

- Increase ≥ 1 g/dL
- Increase ≥ 1.5 g/dL

The number and percentage of subjects meeting the following selected change in HbF categories will be tabulated by treatment arm:

- Increase $\geq 3\%$

Scatter box-whisker plots for the mean change in Hb and HbF concentrations over continuous 12-week intervals from Week 12 to Week 24 and Week 24 to Week 36 in the absence of transfusions will be provided by treatment arm.

In addition, the change in mean Hb and HbF concentrations over continuous 12-week intervals from Week 12 to Week 24, and Week 24 to Week 36 in the absence of transfusions will be assessed using ANCOVA models with Baseline value as a covariate. Summary statistics for observed values at Baseline, Weeks 12-24, and Weeks 24-36, and change from Baseline to Weeks 12-24 and 24-36 will be presented. LSMean estimates and 95% CIs will be presented for each active arm and placebo at Weeks 12-24 and Weeks 24-36. The LSMean difference estimates and associated 95% CIs and p-values at Weeks 12-24, and Weeks 24-36 will also be reported for each active arm compared to placebo and the combined active arms compared to Placebo.

Iron Chelation Therapy and Serum Ferritin Endpoints

The mean change from Baseline to Week 36 for iron chelation therapy daily (ICT) dose and serum ferritin will be assessed for the NTDT Population similar to above in section 13.6.4.1 for the TDT Population.

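### The CTCAE anemia grade shift is a poor measure of Hb worsening here: blind below 8.0 g/dL, noisy just above it, ambiguous for TDT, and no planned table counts subjects whose Hb falls

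*SAP*

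**What the plan says.** SAP Section 9.0 lists as a primary safety measure the "Incidence of subjects with a post-Baseline clinically significant worsening in the CTCAE laboratory grade for a lab parameter". Section 13.6.2.2 gives the display: "Shift tables will be used to summarize the shift from Baseline grade to maximum CTCAE grade". It covers the Appendix 4 parameters. Any post-baseline result counts, including unscheduled ones, and no confirmation is required.

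The anemia row of Appendix 4 uses fixed cut-offs. Grade 2 is "<10.0 – 8.0 g/dL; <6.2 – 4.9 mmol/L; <100 – 80g/L". Grade 3 is "<8.0 g/dL; <4.9 mmol/L; <80 g/L; transfusion indicated". Grade 4 is "Life-threatening consequences; urgent intervention indicated", with no Hb value. The same appendix grades ALT, AST, ALP, bilirubin and GGT against the subject's own level when Baseline is abnormal, for example "1.5 - 3.0 x baseline if baseline was abnormal". Anemia has no such rule.

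Protocol Section 8.1, criterion 10, requires NTDT subjects to have Hb of at most 10.0 "g/dL at Screening; the screening Hb sample must be collected 7 to 28 days prior to randomization"; no lower limit is given. Criterion 4 defines TDT subjects as regularly transfused.

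On categorical Hb change, SAP Section 13.6.4.3 says "The number and percentage of subjects meeting the following selected change in Hb categories will be tabulated by treatment arm". The categories listed are rises of at least 1 and at least 1.5 g/dL. Table 5 in Section 13.6.2.2 covers hepatic function, renal function and platelets, and has no Hb row.

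**The concern.** Hb is the central laboratory value in an anemia trial whose primary objective is safety. Nearly every NTDT subject starts at Grade 2 or 3 by eligibility, so the anemia grade can move in only one useful place, across 8.0 g/dL. Below that line no laboratory value can raise the grade. Just above it, one ordinary low reading among many is enough.

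For TDT, read literally, every eligible subject already meets the transfusion clause and so sits at Grade 3 at Baseline. Read on values alone, the grade can move. The SAP does not choose, although in the same appendix it operationalises the anticoagulation qualifier for INR with an ATC code. Two programmers could produce different TDT tables.

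At stake is whether a harmful Hb fall in some subjects on drug would appear in a planned count by arm, particularly among the most anemic subjects.

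**Working it through.** The plan gives no figure of its own to reproduce here.

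**1. Apply the Appendix 4 cut-offs (no assumptions needed)**

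| Baseline to worst Hb (g/dL) | Fall | Grade | Worsening? |
|---|---|---|---|
| 7.9 to 5.0 | 2.9 | 3 to 3 | no |
| 8.0 to 7.9 | 0.1 | 2 to 3 | yes |
| 9.9 to 8.0 | 1.9 | 2 to 2 | no |
| 9.9 to 7.9 | 2.0 | 2 to 3 | yes |

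**2. Chance of crossing 8.0 with no true change**

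Protocol Table 3 schedules 11 post-baseline NTDT hematology samples (Weeks 1, 4, 8, 12, 16, 20, 24, 28, 32, 36 and 40). With true level μ, within-subject SD s (assumed, since the documents give none) and independent errors, the chance that at least one value is below 8.0 is

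P = 1 − [1 − Φ((8.0 − μ)/s)]^11.

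For example, μ = 8.5 and s = 0.5 gives Φ(−1) = 0.159 and P = 1 − 0.841^11 = 0.85.

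| True Hb | s = 0.3 | s = 0.5 |
|---|---|---|
| 8.2 | 96% | 99% |
| 8.5 | 42% | 85% |
| 9.0 | 0.5% | 22% |
| 9.5 | 0% | 1.5% |

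The noise is concentrated just above the cut. From about 9 g/dL upward, a shift to Grade 3 is mostly real when s is 0.5 or less.

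**3. Whole NTDT population, by simulation**

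Assumptions: true Hb normal with mean 8.5 (range 8.0–9.0) and between-subject SD 1.0 (not varied); screening value at most 10.0; s = 0.4 (range 0.3–0.5); one Baseline value and 11 post-baseline values rounded to 0.1; no transfusions.

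- At Grade 3 at Baseline: 33% (19–50%). Able to worsen on laboratory values: 0%.
- No true change, Grade 2 starters crossing: 40% (21–62%) with independent errors; 27% with visit correlation 0.8 (central case).
- No true change, starters at 8.0–8.4 crossing: 77% (central case).
- True fall of 1.0 g/dL, Grade 2 starters crossing: 91% (central case).

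**4. A Baseline-relative count on the same model**

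Rule: a fall of at least 1.5 g/dL from own Baseline on two consecutive samples.

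- No true change: 0.4% (0–2%) counted.
- True 1.5 g/dL fall: 61% found in Grade 3 starters, 80% in the others.
- True 2.0 g/dL fall: 92% and 98%.

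**5. Why the count needs a transfusion rule**

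Section 13.6.4.3 leaves Hb values within 8 weeks after a transfusion out of the NTDT means. Suppose, purely for illustration, that subjects are transfused when a sample is below 7.0 g/dL (range 6.0–7.5). If the two samples must be adjacent visits, detection of a true 2.0 g/dL fall drops from 96% to 34% (71–16%), and in Grade 3 starters to 0% (22–0%). If consecutive means the next usable sample, it is 90% (94–89%).

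**The case against.** A reader might infer that the grade cannot measure Hb worsening at all in this trial. The documents do not support that. Subjects starting near 9–10 g/dL can show a genuine Grade 2 to 3 shift, and on the assumed model a true 1.0 g/dL fall moves 91% of Grade 2 starters against 40% with no effect. Random crossings also occur on placebo, so they dilute the comparison and do not bias it.

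Nor would falls be invisible elsewhere. Section 13.6.2.2 summarises Hb change by visit and arm with quartiles and minimum, and provides listings, including one of abnormal values. A clinically significant result becomes an AE, graded and counted by arm, so a subject at Grade 3 at Baseline can still appear with an anemia TEAE. Section 13.6.4.3 plots Hb change by arm. The TDT analyses cover pre-transfusion Hb and units transfused. All of this stands. None of it counts subjects with an Hb fall, however: AE reporting depends on investigator judgement, and the Section 13.6.8 shift plot, which includes Hb, uses the post-baseline maximum and so shows rises.

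The primary measure refers to clinically significant worsening, which the SAP does not define for Hb. The crossing rates above therefore describe the shift table; they carry over to the incidence measure only if every shift is counted.

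It is also tempting to say that all TDT subjects are fixed at Grade 3. That holds only if the transfusion clause is applied when values are graded. Section 13.6.2.2 speaks of grading laboratory values, and Section 13.4 expects pre-transfusion Hb on both sides of 9 g/dL. What remains is an ambiguity.

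Finally, the Hb mean and SDs are assumed; the 8.5 g/dL cut in Section 13.4 is a category boundary, not a mean.

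**Conclusion.** The concern holds in a limited form. The ceiling below 8.0 g/dL, the reliance on single unconfirmed values, the unspecified TDT rule and the absence of any count of Hb falls can all be read directly from the SAP. The percentages rest on the assumed means and SDs. The crossing rates are highest when visit errors are independent and fall with correlation. The grade shift remains informative for NTDT subjects starting well above 8.0 g/dL and should stay, but it should not be the only subject-level count of Hb worsening. This is a cheap improvement and not a threat to the trial's validity.

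**What to change.** In SAP Section 13.6.2.2, Table 5, add a descriptive row, n and % by arm: Hb fall of at least 1.5 g/dL from own Baseline on two consecutive usable samples. The size mirrors the SAP's existing category for increases.

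- Define consecutive as the next usable sample.
- For NTDT, do not use values within 8 weeks after a transfusion, and show the number of subjects transfused post-baseline beside the row, so that falls leading to transfusion are not hidden.
- For TDT, use pre-transfusion Hb where a historical baseline exists, and report the number evaluable.

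In Appendix 4, state that laboratory anemia grades use the Hb value only. Report Hb grade worsening among subjects below Grade 3 at Baseline.

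The cost is SAP wording and one table row, with no new data collection. The downsides are a further Hb definition beside the CTCAE grade, and incomplete TDT baselines, because Protocol Section 11.1.5 collects historical pre-transfusion Hb only where available. The 1.5 g/dL size and the two-sample rule are choices, and another prespecified Baseline-relative definition could serve.

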Appendix 5 Regions

The following geographic regions include the countries listed below:

Europe/North America:

Denmark
France
Italy
Greece
Netherlands
Georgia
Turkey
UK
US

Asia/Africa:

Israel
Lebanon
Malaysia
Tunisia
Morocco

Appendix 6 Shell Column Headers

For shells with all treatment arms and a total column, the column headers will be displayed as:

Placebo (N=XX)	IMR-687 200/300 mg (N=XX)	IMR-687 300/400 mg (N=XX)	IMR-687 Pooled Dose (N=XX)	Total (N=XX)
-------------------	------------------------------	------------------------------	-------------------------------	-----------------

For shells with all treatment arms and a pooled active arms column, the column headers will be displayed as:

Placebo (N=XX)	IMR-687 200/300 mg (N=XX)	IMR-687 300/400 mg (N=XX)	IMR-687 Pooled Dose (N=XX)
-------------------	------------------------------	------------------------------	-------------------------------
